#### **8.2.3.2. Short Form Health Survey**

A score will be calculated for each of the 8 scales in SF-36. Each scale score ranges from 0 to 100, with higher score reflecting less disability. The partially missing scores may be imputed as described in [Appendix 3](#) and used in the summary and analysis. 2 overall scores will be further derived: Physical Component Summary score (PCS) and Mental Component Summary score (MCS). The summary scores range from 0 to 100, with higher scores indicating better levels of function and/or better health. See scoring algorithm in [Appendix 3](#). All 8 scale scores and 2 overall scores will be summarized by visit. Change from Baseline in scale scores, PCS, and MCS will be analyzed and reported using the same MMRM and ANCOVA model as specified for the change in EQ-5D Summary Index in [Section 8.2.3.1](#).

### **8.2.3.3. Female Sexual Distress Scale**

The Female Sexual Distress Scale (FSDS) is a validated instrument that measures sexually related personal distress in women. The FSDS is a 13-item self-administered questionnaire that addresses different aspects of sexual distress. Every item requires an answer that is then rated as 0–4 (never [0], rarely [1], occasionally [2], frequently [3], or always [4]). The total score ranges from 0 to 52, and provides a measure of sexual distress, with a higher score corresponding to a higher level of sexual distress. No missing dimension will be imputed.

FSDS total score will be summarized by treatment and by visit descriptively. Change from Baseline in FSDS total score will be analyzed and reported using the same MMRM and ANCOVA model as specified for the change in EQ-5D Summary Index in [Section 8.2.3.1](#).

In addition, FSDS total score will be classified as '<11' and '>=11'. This categorical data will be summarized with the frequency and percentage of subjects by treatment group at each scheduled visit. In addition, this categorical data will be summarized in shift tables comparing the results at post-treatment study scheduled visits with those at the baseline visit.

### **8.2.4. Composite Score of the Vulvovaginal Signs and Symptoms**

The composite score of the vulvovaginal signs and symptoms and Change from Baseline values to Week4, Week 8, Week 12, Week 24 (TOC), and Week 36 (EOFU) will be summarized by treatment and by visit descriptively.

The composite score of the vulvovaginal signs and symptoms will be classified as '0', '1', '2', and '>=3'. This categorical data will be summarized with the frequency and percentage of subjects by treatment group at each scheduled visit. When there are multiple values within a visit, the worst value will be taken (worst being the maximum value of the composite score of the vulvovaginal signs and symptoms). All analysis will be performed based on the ITT, mITT, and PP sets. The similar analyses will be performed for below 2 categorizations of the composite score of the vulvovaginal signs and symptoms: '<7, >=7' and '4 - 7', '8 - 12', and '>=13'.

A listing will be provided to present the signs and symptoms score and mycological outcome for all subjects in the ITT set. Assessments that are not done will be presented in the data listing with a missing value.

Signs of VVC will be defined as the presence of erythema, edema, or excoriation. Symptoms of VVC will be defined as itching, burning, or irritation.

Each vulvovaginal sign will be objectively scored based on severity as follows:

- 0 = none (complete absence of any signs or symptoms);
- 1 = mild (slight);
- 2 = moderate (present);
- 3 = severe (marked, intense).

Each vulvovaginal symptom will be objectively scored based on severity as follows:

0 = none (I have no discomfort);

1 = mild (I have some discomfort, but it does not bother me much);

2 = moderate (I have discomfort, which is annoying, but not enough to affect what I am doing);

3 = severe (I have discomfort, which is annoying enough to affect what I am doing).

The composite score of the vulvovaginal signs and symptoms will be calculated according to the following rules and this scale has a total possible score of 18.

- If all items of the vulvovaginal signs and symptoms have been scored, the composite score is calculated as the sum of the individual scores of all 3 items of signs and 3 items of symptoms;
- If any sign or symptom is not done, the composite score will not be calculated and treated as a missing data except at Week 4, Week 8, and Week 36 (EOFU);
- Subjects who have no suspicion of a potential recurrence are not required per protocol to have a vaginal examination at Week 4, Week 8, and Week 36 (EOFU), therefore signs are not considered missing when subjects are free of symptoms and there is not suspicion of a potential recurrence. For subjects who do not present symptoms and have no suspicion of a potential recurrence at Week 4, Week 8, and Week 36 (EOFU), the total sign score and the composite score of the vulvovaginal signs and symptoms at Week 4, Week 8, and Week 36 (EOFU) will be calculated as zero. Otherwise, the composite score will not be calculated and treated as a missing.

## 9. Safety Analysis

Safety analyses will be performed on all subjects in the safety set, unless otherwise specified. Analyses will be based on adverse events, vital signs, clinical laboratory assessments, and abbreviated physical examination findings. Safety analyses in general will be descriptive and will be presented in tabular format with the appropriate summary statistics by treatment group.

Individual subject listings will be provided to support the tables.

### 9.1. Adverse Events

An AE is any untoward medical occurrence associated with the use of a drug in humans, whether or not considered drug related. An AE can therefore be any unfavorable and unintended sign (including an abnormal laboratory finding), symptom or disease temporally associated with the use of a study drug/study intervention, whether or not related to the study drug/study intervention.

A prior adverse event (PAE) is defined as adverse event whose start date is before the date of the first dose of study treatment. For subjects who didn't take study treatment, all AEs will be identified as PAE. A Summary of the total number of PAE and the number and percentage of subjects with at least one PAE will be provided by SOC and PT based on all screened patients. Besides, a subject listing will be presented for all the prior adverse events.

A TEAE is defined as any event does not present before exposure to study drug or any event already present that worsens in either intensity or frequency after exposure to study drug.

For the purpose of inclusion in TEAE tables, incomplete AE start and end dates will be imputed as follows:

Incomplete onset dates (where UK and UNK indicate unknown or missing day and month respectively):

- UK-*MMM*-*YYYY*: If the month and year are different from the month and year of the date of first dose, assume 01-*MMM*-*YYYY*. If the month and year are the same as the month and year for the date of first dose, and the end date (after any imputation) is on or after the date of first dose, then assume the date of first dose. If the month and year are the same as the date of first dose, and the end date (after any imputation) is prior to the date of first dose, then assume the end date for the start date.
- *DD*-UNK-*YYYY*/UK-UNK-*YYYY*: If the year is different from the year of the date of first dose, assume 01-JAN-*YYYY* of the collected year. If the year is the same as the date of first dose year, and the end date (after any imputation) is on or after the date of first dose, then assume the date of first dose. If the year is the same as the date of first dose, and the end date (after any imputation) is prior to the date of first dose, then assume the end date for the start date.

Incomplete end dates (where UK and UNK indicate unknown or missing day and month respectively):

- UK-MMM-YYYY: Assume the last day of the month;
- DD-UNK-YYYY/UK-UNK-YYYY: Assume 31-DEC-YYYY.

The missing onset dates will be imputed as the date of first dose of study drug. The missing end date will be imputed as the subject's last visit date.

All adverse events will be classified by SOC and PT according to the Medical Dictionary for Regulatory Activities (MedDRA, Version 19.1 or higher).

An overview summary of the number and percentage of subjects with any TEAE, serious TEAE, treatment-related TEAE, treatment-related serious TEAE, TEAE leading to study treatment discontinuation, TEAE leading to study discontinuation, and AE leading to death will be provided by treatment group and study period (prior or on TOC visit, after TOC visit but prior or on EOFU visit, and entire study).

All AEs will be presented in a listing.

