16.10 Adverse Event Collection Timeframe

AEs and SAEs will be recorded from the time the ICF is signed (Screening) through Week 24 (TOC). New AEs starting after Week 24 and until Week 36 will be recorded only if they led to the use of other antifungal medications or topical vaginal treatment, or if they are a vaginal bacterial or parasitic infection, or if they are deemed related to the previously administered study drug.

All AEs reported by the subject or observed by members of the clinical staff will be evaluated by the PI or qualified designee. The PI will attempt, if possible, to establish a diagnosis based on presenting signs and symptoms. The nature of the AE, time of onset relative to study drug administration, duration, severity, and relationship to treatment should be determined. Details of any corrective treatment must be recorded in the eCRF. The PI will determine whether any changes have occurred in baseline signs and symptoms. All AEs and SAEs will be collected in the eCRF.

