### 3.3. Treatments

#### Acute Phase

Subjects who meet all study eligibility criteria at screening will enter the Acute Phase of the study and will receive oral fluconazole, as follows:

- Oral fluconazole 150 mg QD on Days -14, -11 and -8

The first dose of fluconazole will be administered on Day -14 at the study site, after all other visit procedures have been done. Subjects will self-administer the remaining doses at home.

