#### **4.3. Analysis Set**

Intent-to-Treat (ITT) Set: All randomized subjects who received at least one dose of study drug (ibrexafungerp or placebo).

Modified Intent-to-Treat (mITT) Set: All randomized subjects who received at least one dose of study drug (ibrexafungerp or placebo), who have a confirmed mycological culture for yeast at Screening and a negative culture for yeast at Baseline (Day 1).

Per-Protocol (PP) Set: All mITT subjects who did not have major protocol deviations likely to affect study efficacy and who have available data at the TOC visit. Note that subjects who discontinue due to a study-drug-related AE will be classified as failures for the analyses of efficacy under the PP population.

Safety Set (SS): All randomized subjects who received at least one dose of study drug (ibrexafungerp or placebo) and who have at least one post-baseline evaluation.

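### SAP 9.1 dates a wholly missing adverse-event onset to the first dose without checking the end date, so an event that stopped before Day 1 can be tabulated as treatment-emergent

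*SAP*

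**What the plan says.** SAP 9.1 introduces its date rules with a stated purpose: "For the purpose of inclusion in TEAE tables, incomplete AE start and end dates will be imputed as follows". It then treats two situations differently.

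- **Onset partly known** (day unknown, or month unknown with or without the day). Where the known part matches the first dose, the end date is consulted. If the event was still present on or after the first dose, onset becomes the first-dose date. If the month or year matches "and the end date (after any imputation) is prior to the date of first dose, then assume the end date for the start date".
- **Onset wholly missing.** "The missing onset dates will be imputed as the date of first dose of study drug". No condition is attached.

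The two classifications that depend on these dates are in the same section. For prior events: "A prior adverse event (PAE) is defined as adverse event whose start date is before the date of the first dose of study treatment". For treatment-emergent events: "A TEAE is defined as any event does not present before exposure to study drug", or one already present that worsens after exposure.

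Protocol 16.10 sets the collection window: "AEs and SAEs will be recorded from the time the ICF is signed (Screening) through Week 24 (TOC"). That window includes the open-label run-in, for which the SAP's treatment section gives "Oral fluconazole 150 mg QD on Days -14, -11 and -8".

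SAP 13.4.9.1, for the nested sub-study, repeats the wholly-missing rule word for word.

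**The concern.** The SAP recognises, for partial dates, that a recorded end date before the first dose settles the matter: the event cannot have begun on randomized drug. It drops that safeguard when the onset is blank, although the end date is just as informative then. The result is a record whose onset is later than its end and a run-in event counted among events emerging on blinded drug. It also drops out of the prior-event table built to hold it. At stake is the accuracy of the treatment-emergent and prior-event tables, and of the main-study table by relationship and duration in SAP 9.1.2.

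**Working it through.** The documents state no figure for this point, so there is none to reproduce. The check applies the rule to example events.

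**Inputs**

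- Onset when wholly missing: first-dose date (SAP 9.1).
- First dose: Day 1. SAP 4.3 ties study drug to the randomized products ("All randomized subjects who received at least one dose of study drug (ibrexafungerp or placebo")), and Protocol 14.0 counts days from the first double-blind dose.
- There is no Day 0 (SAP 4), so Day -8 lies 8 calendar days before Day 1.
- Duration = end date - start date + 1, tabulated as 1 day, 2 days, or 3 days and more (SAP 9.1.2).
- A prior event needs a start date before the first dose (SAP 9.1).

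**Wholly missing onset, known end date**

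| Event ends | Duration as written (onset Day 1) | Class as written | With the end-date check added |
|---|---|---|---|
| Day -14 | -14 + 1 = -13 | treatment-emergent, no duration class | onset Day -14, 1 day, prior event |
| Day -11 | -11 + 1 = -10 | treatment-emergent, no duration class | onset Day -11, 1 day, prior event |
| Day -8 | -8 + 1 = -7 | treatment-emergent, no duration class | onset Day -8, 1 day, prior event |
| Day -4 | -4 + 1 = -3 | treatment-emergent, no duration class | onset Day -4, 1 day, prior event |
| Day -1 | -1 + 1 = 0 | treatment-emergent, no duration class | onset Day -1, 1 day, prior event |
| Day 1 | 0 + 1 = 1 | treatment-emergent, 1 day | unchanged |
| Day 5 | 4 + 1 = 5 | treatment-emergent, 3 days and more | unchanged |

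Every end date before Day 1 gives an onset after the end and a duration of zero or less. An imputed onset equal to the first-dose date is not before it, so the event fails the start-date test for a prior event.

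**The same event under both rules** (illustrative dates: first dose 15 March, event ended 8 March). If the site records only the month of onset as March, the partial-date rule sets onset to 8 March and the event is prior, lasting 1 day. If the onset is blank, onset becomes 15 March, the event is treatment-emergent, and its duration is 8 - 15 + 1 = -6 days.

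**Who can be affected.** Only subjects who took study treatment, since SAP 9.1 makes every event of an undosed subject a prior event. Only events with a blank onset and an end date that is before Day 1 after any imputation. If the end date is also missing it is set to the last visit, which for a subject seen on or after Day 1 causes no reversal.

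**Sub-study.** SAP 13.4.9.1 has no prior-event definition, and SAP 13.4.9.1.2 has no duration table, so those two consequences are confined to the main study. What remains is entry into the treatment-emergent tables, to which all sub-study summaries are restricted. Whether run-in events are in the sub-study data is not settled: Protocol 21.3.10.16, footnote k of Sub-Study Table 1 and 21.3.14.6.1 record events from main-study consent, while 21.3.12.3 records them from Baseline.

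**The case against.** The strongest reply is that the SAP's definition already excludes these events: one that stopped before exposure was present beforehand and did not worsen afterwards, whatever onset is imputed. A careful programmer could rely on that. The definition does conflict with the rule, but the SAP says the imputation serves entry into the treatment-emergent tables and writes no override. The prior-event test also uses the start date alone.

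A second reply is that study drug might include fluconazole, as Protocol 12.3 lists it; the first dose would then be Day -14 and the problem would largely vanish. SAP 4.3 points the other way, and SAP 7.2.1.1 names the first fluconazole dose separately.

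A third is that defaulting to the first dose is conservative. That is fair when timing is unknown, but not when a recorded end date shows the event was over.

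On size, much of the reply stands. Protocol 16.10 asks sites to determine time of onset and diaries are reviewed on Day 1, so a wholly blank onset should be uncommon. Safety has no formal testing, and all events are listed, so reversed dates would be visible.

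A reader might infer that every run-in event with these dates is misclassified. Undosed subjects' events are not. A reader might also infer that such events are attributed to ibrexafungerp. Treatment-emergent is a label of timing; attribution is the investigator's relationship assessment, and SAP 9.1.1 counts an event as related by default only if that field is blank too.

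**Conclusion.** The rule is wrong as written: for a defined set of records it gives impossible dates and a classification that contradicts the SAP's own definition. The error runs one way, from prior to treatment-emergent, but it is minor. The documents give neither the number of run-in events nor the share lacking an onset, so no percentage can be supported; the count is probably small. In the main study a reader might suspect a distorted comparison of arms, but run-in events precede randomization, so the extra events should be about balanced. In the single-arm sub-study there is no comparator, yet the point arises only if events are collected from consent. The conclusion assumes that the first dose means the first ibrexafungerp or placebo dose and that the imputation sentence is programmed literally.

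**What to change.** In SAP 9.1 and 13.4.9.1, replace the sentence on missing onset dates with: *A completely missing onset date is imputed as the date of first dose of study drug, unless the end date (after any imputation) is before the date of first dose, in which case the end date is used as the onset date.* This reuses the partial-date logic and leaves events ending on or after Day 1 unchanged. Separately, reconcile the protocol's two statements of when sub-study event collection starts. For the imputation rule, the cost is one sentence in two sections and one line of code, with no new data.

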### **9.1.1. Treatment-Emergent Adverse Events**

Summaries of the total number of TEAEs and the number and percentage of subjects with at least one TEAE will be provided by treatment and study period (prior or on TOC visit, after TOC visit but prior or on EOFU visit, and entire study). Treatment-emergent AEs will be presented by SOC and PT. At each level of subject summarization, a subject is counted once if the subject reported one or more events. Percentages will be calculated out of the number of subjects in the safety set.

The summary of TEAEs will be presented in alphabetical order of SOC. Within each SOC, PTs will be sorted in descending order from the PT with the highest total frequency (that is, summed across all treatment groups) to the PT with the lowest total frequency. If the total frequency for any two or more PTs is equal, the PTs will be presented in alphabetical order.

The summarization described above will also be repeated for the following:

- Serious Adverse Events;
- Treatment-Related Adverse Events;
- Treatment-Related Serious Adverse Events;
- Adverse Events Leading to Dose Interruption.

The adverse events with a missing relationship will be considered as "Treatment Related" in the tables.

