18.0 Analytical Plan

All statistical analysis will be performed using SAS® version 9.3 or later, unless otherwise stated. All statistical tests will be two-sided and interpreted at a 5% significance level.

Descriptive statistics (i.e., mean, standard deviation, median, minimum, maximum, etc.) will be provided for all continuous variables; frequencies and percentages will be tabulated for incidence and categorical variables. For parameters measured over time, observed values and changes from baseline will be described for each time point.

The Mycologically Proven Recurrence and Mycological Eradication rates will be described by baseline *Candida* species, when the number of isolates per species allows.

The percentage of subjects with Mycologically Proven Recurrence will be described by number of VVC episodes in the 12 months prior to randomization.

All analyses will be presented by treatment group, as appropriate. Unless otherwise stated, data will be analyzed as is with no imputation. No adjustment for multiplicity will be employed.

A Statistical Analysis Plan (SAP) describing all final statistical analyses in detail will be provided as a separate document. The SAP will be finalized prior to the unblinding of the study treatments for analysis.

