18.1 Sample Size Determination

The primary endpoint of the study is the percentage of subjects with documented Clinical Success up to TOC (Week 24). Assuming response rates of 65% and 43% for ibrexafungerp and placebo, respectively; 90% power; and an alpha level of 0.05, approximately 240 subjects randomized at a 1:1 ratio are needed to declare a difference between ibrexafungerp and placebo at Week 24 based on Fisher's Exact test.

In order to be randomized, a subject should have achieved the proposed significant resolution of signs and symptoms (total composite score ≤ 2 on the VSS Scale) after receiving fluconazole therapy for an acute episode and have a positive culture for *Candida* spp. from the sample collected at Screening. It is estimated that approximately 320 subjects will need to enter the Acute Phase to provide 240 subjects randomized to the Prevention of Recurrence Phase. Enrollment into the Acute Phase will be discontinued when approximately 240 subjects have been randomized.

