#### 4. General Statistical Considerations

Continuous data will be described using descriptive statistics (i.e. n, mean, standard deviation (SD), median, minimum, and maximum). Categorical data will be described using the subject count and percentage in each category. For the summary statistics of all numerical variables unless otherwise specified, minimum and maximum will be displayed to the same level of precision as reported. Mean and median will be displayed to one level of precision greater than the data collected. Standard deviation / standard error will be displayed to two levels of precision greater than the data collected. P-values will be rounded to three decimal places. If a p-value is less than 0.001 it will be reported as “<0.001.” If a p-value is greater than 0.999 it will be reported as “>0.999.” Data will be displayed in all listings sorted by treatment group.

Subjects will be identified in the listings by the subject identification number concatenated with the investigator number.

When count data are presented, the percentage will be suppressed when the count is zero in order to draw attention to the non-zero counts. A row denoted “Missing” will be included in count tabulations where specified on the shells to account for dropouts and missing values. The denominator for all percentages will be the number of subjects in that treatment within the analysis set of interest, unless otherwise specified.

Unless otherwise specified, baseline will be defined as the last non-missing assessment prior to or on the date (and time if appropriate) of the first dose of study drug. Change from baseline is defined as post-baseline value – baseline value.

The study day will be calculated as follows:

If the assessment date occurs on or after the date of the first dose of study drug:

$$\text{Study day} = \text{assessment date} - \text{first dose date} + 1.$$

If the date of interest occurs before the date of the first dose of study drug:

$$\text{Study day} = \text{assessment date} - \text{first dose date}$$

There is no study day 0.

All analyses will be conducted using SAS Version 9.3 or higher. All statistical tests will be two-sided and interpreted at a 5% significance level.

This statistical analysis plan is created for the main study. Regarding the detailed description of the statistical analysis of the nested sub-study, please refer to the [Appendix 4](#).

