### **7.1.3. Rescue Antifungal Medications**

The number and percentage of subjects who took rescue antifungal medication, prior or on TOC visit, after TOC visit but before or on EOFU visit, will be presented for the ITT and mITT sets.

A by-subject listing of rescue antifungal medications will be provided.

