### **9.2.2. Events of Clinical Interest**

The frequency and percentage of subjects with the following elevations will be summarized at any post-baseline visit:

- ALT or AST  $> 8 \times$  the upper limit of normal (ULN);
- ALT or AST  $> 5 \times$  ULN for more than 2 weeks or accompanied by total bilirubin  $> 2 \times$  ULN.

A listing will be provided for the above elevations, including the actual measurement of ALT, AST, and total bilirubin, and their reference high limits.

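### Post-TOC adverse-event and rescue percentages, and the ALT/AST event percentage, divide by the full analysis set, so women not observed for the period or test count as event-free

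*SAP*

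**What the plan says.** **Adverse events.** SAP 9.1.1 breaks the tables down by "study period (prior or on TOC visit, after TOC visit but prior or on EOFU visit, and entire study"), and SAP 9.1 uses the same three periods for the overview table. SAP 9.1.1 then fixes one denominator for all of them: "Percentages will be calculated out of the number of subjects in the safety set".

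**Rescue antifungals.** SAP 7.1.3 splits use at TOC, with the later part described as "after TOC visit but before or on EOFU visit, will be presented for the ITT and mITT sets". It names no denominator of its own.

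**Liver events.** SAP 9.2.2 states: "The frequency and percentage of subjects with the following elevations will be summarized at any post-baseline visit". It also names no denominator. SAP 9 places safety analyses in the Safety Set.

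**Default rule.** SAP 4 covers both silent sections: "The denominator for all percentages will be the number of subjects in that treatment within the analysis set of interest, unless otherwise specified".

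**Who is in the sets.** Under SAP 4.3, ITT entry needs randomisation and one dose. The Safety Set adds any one evaluation after baseline. mITT adds culture conditions at Screening and Baseline. None requires a woman to reach TOC or to have a post-dose blood sample.

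**Leavers.** Protocol 11.3 has women who leave the study by Week 24 undergo the TOC procedures when they leave. Protocol 11.4 says early leavers from randomised treatment are not replaced.

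**Blood draws.** Protocol 14.12 and the visit schedule (Protocol Table 2, SAP Appendix 1) give Week 12 as the only routine post-dose draw; other samples are as needed. The Week 24 description in Protocol 10.1.1.3.1 lists no laboratory sample, yet Protocol 9.3 and 10.1 name safety laboratory tests at TOC.

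**The concern.** A woman who left the study at Week 8 has no follow-up period. No post-TOC adverse event or rescue course can be recorded for her, but she stays in the denominator of the post-TOC column and is in effect counted as event-free there. Likewise, a woman who left after Week 4 can be in the Safety Set with no post-dose ALT or AST value, and she counts as having no elevation.

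The post-TOC columns are the planned view of safety and rescue use after dosing stops. The background sections of both documents suggest that a fungicidal drug may give more lasting benefit after therapy ends, so post-TOC rescue use will be read with interest. Liver events are likely to be few, and the denominator then largely determines the printed percentage.

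Elsewhere the plan deals openly with non-observation. Unobserved clinical responses are failures (SAP 4.4.1), with a sensitivity analysis that removes imputed outcomes (SAP 8.1.1). Time to recurrence is censored, and recurrence counts are repeated in women who completed the visit (SAP 8.2.1). The safety and rescue tables have no counterpart, and in them non-observation lowers the reported rate.

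**Working it through.** **The plan's own figure.** The documents state no figure for these percentages. The only relevant number is the sample size, which is not in dispute and supplies the 120 per arm used below. Protocol 18.1 gives the inputs: "Assuming response rates of 65% and 43% for ibrexafungerp and placebo, respectively; 90% power; and an alpha level of 0.05". The planned total there is 240, split equally between the two arms. Protocol 18.0 adds: "All statistical tests will be two-sided and interpreted at a 5% significance level". Fisher power is the sum, over all pairs of success counts whose exact two-sided p-value is at most 0.05, of Bin(x1; 120, 0.65) × Bin(x2; 120, 0.43). Full enumeration gives 90.9%, which agrees with the stated 90%.

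**Formula.** Let N be the set size in an arm, n the number observed in the period (or tested), E the number with an event, r = E/n, and d = 1 − n/N. Then

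printed percentage = E/N = (E/n) × (n/N) = r × (1 − d).

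This is below r whenever d > 0.

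**Inputs that are assumed.** The documents give no dropout rate, overall or by arm, and the sample size section states no dropout allowance. The values of d, r and the event counts below are illustrations.

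| d (assumed) | n of 120 | printed if r = 10% | printed if r = 30% | 12 events: full set | 12 events: observed |
|---|---|---|---|---|---|
| 10% | 108 | 9.0% | 27% | 10.0% | 11.1% |
| 20% | 96 | 8.0% | 24% | 10.0% | 12.5% |
| 30% | 84 | 7.0% | 21% | 10.0% | 14.3% |

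For a single liver event, 1/120 = 0.83%. With 96 women tested, 1/96 = 1.04%.

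**Between arms.** With equal r in both arms, the apparent ratio of ibrexafungerp to placebo is (1 − d_ibrexafungerp)/(1 − d_placebo).

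- 10% v 20% gone: 0.90/0.80 = 1.125
- 20% v 10% gone: 0.80/0.90 = 0.89
- 10% v 10% gone: 0.90/0.90 = 1.00, although both percentages are still lower than r

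**The case against.** The case for leaving the tables alone has several parts.

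- **Full-set incidence is conventional.** Events over all treated women keeps the randomised denominator. It is low only against a different target, the risk among women who stayed, and that group is selected after randomisation. This stands. The smaller denominator is not an unbiased comparison, and the ratios above assume equal risk among the observed women. It is why both figures should be shown.
- **Nothing formal depends on it.** Protocol 18.7.2 plans no formal safety analysis, SAP 9 calls the safety analyses descriptive in general, and SAP 7.1.3 plans only counts and percentages. This stands and limits the weight of the point.
- **A reader can partly recover the rates.** SAP 5.1 tabulates TOC and study completion, by-subject listings are planned, and Kaplan-Meier curves run to the end of follow-up with early leavers censored. This stands in part. The disposition table is for ITT and mITT rather than the Safety Set, attending TOC is not the same as being followed after it, and the curves cover first recurrences, not adverse events or liver tests.
- **The rescue and laboratory denominators are inferred.** A reader might take SAP 7.1.3 and 9.2.2 as setting the full set expressly. They do not. It follows from the SAP 4 default, and the table shells that SAP 4 mentions are not in the documents. A row for missing values would not change the denominator.
- **The same logic reaches the earlier columns.** A woman who leaves at Week 4 is unobserved for the rest of the treatment period. True, but every treated woman entered that period, so the full set is a legitimate crude incidence there. The post-TOC column includes women who never entered it.
- **The size is assumed and small against noise.** In the 27% v 24% case, with 120 per arm, the standard error of the difference is √(0.27×0.73/120 + 0.24×0.76/120), about 5.6 points, against a 3-point shift. This stands for any single comparison. The downward shift itself is systematic.
- **Post-TOC adverse events are selective anyway.** Protocol 14.22 and 16.10 record only certain new events after Week 24. Neither denominator turns that column into full incidence.

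**Conclusion.** The point holds as a modest, inexpensive improvement to descriptive tables. The full-set denominator is explicit for adverse events and follows by default for rescue use and liver events. Each affected percentage is the rate among observed women times (1 − d). For assumed d of 10% to 20%, 10% prints as 9% to 8%, and 10% v 20% dropout with equal observed risk gives 1.125 or 0.89.

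Two stronger readings are tempting and are not supported. One is that the tables flatter ibrexafungerp: the documents give no dropout figure by arm and no reason to expect a difference, the distortion can run either way, and with equal dropout the ratio is unchanged. The other is that the trial's efficacy conclusions are affected: the primary and key secondary analyses do not use these denominators.

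The laboratory part also depends on reconciling the protocol's mentions of laboratory tests at TOC with the visit description and schedule, which show none at Week 24. SAP 11 drops the TOC wording from the safety endpoint but does not settle whether blood is drawn then. If leavers did have blood taken under the TOC procedures, fewer would lack a post-dose result. The post-TOC part would be unchanged.

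**What to change.** 1. In SAP 9.1, 9.1.1 and 7.1.3, for the post-TOC columns only, use as denominator the members of the relevant set (Safety, ITT or mITT) with at least one contact after the TOC visit, or after the Week 24 window if TOC was missed. State that an early-termination visit at or before TOC does not count as such a contact.
2. In SAP 9.2.2 and the laboratory shift tables in SAP 9.2, use subjects with at least one post-baseline value of the analyte.
3. Print that N by arm, keep the full-set percentage as a supplement, and add a note that the observed subset is selected after randomisation.
4. Keep the full set for the columns up to TOC and for the whole study.
5. Reconcile the protocol passages on laboratory testing at TOC.

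The cost is SAP wording, one extra column N and slightly higher reported rates. Items 1 to 4 need no new data. The new N counts women who entered the period, not women followed to Week 36, and the table note should say so.
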